### 8.3 Pregnancy

If a pregnancy occurs, U.S. Pharmacovigilance at Ferring Pharmaceuticals must be informed. Contact details for the follow-up on the course and outcome of the pregnancy should be included. The mother and the fetus must be followed-up at least until the birth of the infant and one month after the birth of the infant. In general, the follow-up will include the course, duration and the outcome of the pregnancy as well as neonatal health. If a pregnancy results in an abnormal outcome (birth defect/congenital anomaly) this must be reported as a serious adverse event to U.S. Pharmacovigilance at Ferring Pharmaceuticals using the Safety Report Form.

## 8.4 Collection, Recording and Reporting of Serious Adverse Events

### SAE Reporting by the Investigator

All SAEs must be reported **immediately** to Ferring U.S. Pharmacovigilance as soon as it becomes known to the Investigator and not later than within 24 hours of their knowledge of the occurrence of an SAE.

The Investigator is responsible for submitting the completed SAE Report Form with the fullest possible details **within 3 calendar days** of his/her knowledge of the SAE to Ferring U.S. Pharmacovigilance using the contact details below.

U.S. Pharmacovigilance, Ferring Pharmaceuticals A/S

E-mail: [[contact]](mailto:[contact])

Fax: [REDACTED]

Completion of the Demographics, Adverse Event Log, Medical History Log and Concomitant Medication Log are mandatory for initial reports and for follow-up reports if any relevant changes have been made since the initial report. Data entries must have been made in the eCRF for Ferring Global Pharmacovigilance to access the information.

Additional information relevant to the SAE such as hospital records, results from investigations, (e.g., laboratory parameters that are not already uploaded in the eCRF), invasive procedures, scans and x-rays, and autopsy results can be faxed or scanned and e-mailed to Ferring Global Pharmacovigilance using the contact details in the section above. In any case this information must be supplied by the Investigator upon request from Ferring. On any copies provided, details such as subject's name, address, and hospital ID number should be concealed and instead subject number should be provided.

The Investigator will supply Ferring and the IRB/REB with any additional requested information such as results of post-mortem examinations and hospital records.

### Expedited Reporting by Ferring

As per Regulations, Ferring will report all adverse events that are **unexpected** to the relevant regulatory authorities within the stipulated timelines.

## **8.5 Follow-up of Adverse Events and Serious Adverse Events**

### **8.5.1 Follow-up of Adverse Events with Onset during the Trial**

During the trial, the Investigator must follow-up on each adverse event until it is resolved or until the medical condition of the subject is stable.

After the subject's last visit, the Investigator must follow-up on any adverse event classified as serious or considered to have a reasonable possible causality to the graft material until it is resolved or until the medical condition of the subject is stable. All such relevant follow-up information must be reported to Ferring. If the event is a chronic condition, the Investigator and Ferring may agree that further follow-up is not required.

### **8.5.2 Collection of Serious Adverse Events with Onset after Last Trial Visit**

If an Investigator becomes aware of an SAE after the subject's last visit, and he/she assesses the SAE to have a reasonable possible causality to the graft material, the case will have to be reported to Ferring, regardless how long after the end of the trial this takes place.

## **9 STATISTICAL METHODS**

Details of the statistical methodology will be provided in a separate statistical analysis plan (SAP).

### **9.1 Determination of Sample Size**

Assuming true success rates of the primary endpoint to be 60% for ABG and 62% for AMPLEX groups, 396 subjects are needed to maintain 85% power to demonstrate non-inferiority of AMPLEX to ABG with a non-inferiority margin of -12% at a type I error rate of 1-sided 5% in a 2:1 randomization (264 for AMPLEX and 132 for ABG). To account for approximately 15% lost to follow-up, a total of 480 subjects (320 for AMPLEX and 160 for ABG) will be randomized.

In this calculation, the true success rate for AMPLEX is assumed to be slightly higher than that for ABG because of the potential benefit for AMPLEX on the absence of significant graft harvest site pain component. The assumption on the true success rate for ABG is made based on the clinical endpoint results in DiGiovanni et al. (2013) and the Augment SSED (2015). These data indicate relatively high success rates for each component at Week 52, and the success rate as a composite endpoint is estimated as approximately 60% under the independence assumption among components.

In the determination of the non-inferiority margin, retaining at least 80% of the assumed success rate in ABG is considered clinically meaningful, because it is inherently linked with substantial benefit of eliminating risks associated with ABG. Therefore, the non-inferiority margin is set to -12%.

In addition, the CT radiographic fusion success rate at 52 weeks for ABG is assumed to be 70% to 75% based on 24 and 36 weeks data available in FDA Orthopaedic and Rehabilitation Devices Division (2011). Assuming that the true CT radiographic fusion success rate for AMPLEX is the same as for ABG, the power to demonstrate the non-inferiority in the CT radiographic fusion success as an independent test with 396 subjects is 79% to 83% at 1-sided 5% significance level using the non-inferiority margin of -12%.

### **9.2 Subject Disposition**

All subjects screened and randomized will be accounted for. All post-randomization discontinuations will be summarized by time of, and reason for, discontinuation. The number of subjects screened and not randomized will be presented.

### **9.3 Protocol Deviations**

The final definition of protocol violations will be determined prior to the database lock. The number and percentage of subjects with important protocol deviations will be summarized.

## **9.4 Analysis Sets**

### **9.4.1 Modified Intention-to-Treat (mITT) Analysis Dataset**

The mITT analysis set will include all randomized subjects who have an attempted fusion of the index joint(s). If a subject becomes ineligible or withdraws prior to the initiation of surgery, the subject will not be included in the mITT analysis set. Once the surgery is initiated, all subjects will be included in the mITT analysis set.

### **9.4.2 Per Protocol (PP) Dataset**

The PP analysis set will consist of all randomized subjects that: [1] complete the fusion procedure and receive either AMPLEX or ABG as assigned, [2] meet critical study eligibility criteria, and [3] have no significant protocol deviations.

### **9.4.3 Safety Dataset**

The safety analysis set comprises all treated subjects and will be analyzed according to the actual treatment received.

## **9.5 Trial Population**

### **9.5.1 Demographics and other Baseline Characteristics**

Descriptive statistics of demographics and other baseline characteristics and medical history will be presented for the mITT, PP and safety analysis sets by treatment group. In addition, summary of demographic and baseline characteristics will be presented by trial site.

### **9.5.2 Medical History, Concomitant Medication and Other Safety Evaluations**

Medical history will be coded by system organ class (SOC) and preferred term (PT) using the most current version of the MedDRA and summarized by SOC, PT, and treatment group for the mITT and Safety analysis sets. Prior and concomitant medications will be coded by the Anatomical Therapeutic Chemical (ATC) classification system and preferred drug name using the World Health Organization Drug Dictionary (WHO-Drug). Prior and concomitant drug usage will be summarized by ATC classification 1st level, ATC classification 2nd level and treatment group for subjects in the mITT and Safety analysis sets.

## **9.6 Endpoint Assessments**

### **9.6.1 General Considerations**

All efficacy analyses will be conducted for the mITT population. The primary and key secondary efficacy endpoints will be analyzed by a fixed-sequence procedure according to the following order to maintain the overall Type 1 error rate to a one-sided 5% for non-inferiority and a one-sided 2.5% for superiority testings.

1. Non-inferiority of AMPLEX to ABG in the primary efficacy endpoint

2. Non-inferiority of AMPLEX to ABG in the key secondary efficacy endpoint
3. Superiority of AMPLEX to ABG in the key secondary efficacy endpoint
4. Superiority of AMPLEX to ABG in the primary efficacy endpoint

Testing procedure will begin with the non-inferiority in the primary efficacy endpoint, and each test will be conducted without adjustment of multiplicity as long as all preceding tests are significant. All other secondary endpoints will be presented with the point estimate of the treatment group difference and the corresponding 2-sided 90% confidence interval.

### **9.6.2 Primary Endpoint**

The primary efficacy endpoint will be the proportion of subjects who meet all of the following criteria for the SPC at 52 weeks:

- Improvement in pain on weight-bearing at fusion site ( $\geq 20$  mm reduction from baseline on 100 mm VAS)
- Absence of significant graft harvest site pain ( $< 20$  mm on 100 mm VAS)
- Improvement in Foot and Ankle Ability Measure Activities of Daily Living subscale (FAAM-ADL) ( $\geq 8$  points improvement from baseline)
- Absence of device related or procedure related SAEs (up to Week 52)
- Absence of secondary surgical or nonsurgical interventions intended to promote fusion (up to Week 52)

Non-inferiority of AMPLEX to ABG will be claimed if the lower bound of the 2-sided 90% CI for the difference of the proportions (AMPLEX minus ABG) is greater than -12.0%. The superiority will be claimed if the lower limit of the 2-sided 95% CI is greater than zero. The CI will be constructed with the normal approximation to the binomial.

The primary efficacy analysis will be based on the mITT analysis set. A sensitivity analysis will be conducted for the PP analysis set. In the analysis on the mITT analysis set, subjects who do not receive the assigned treatment will be analyzed as randomized.

For the primary analysis, the last observation carried forward (LOCF) approach will be used for subjects with missing SPC endpoint at 52 weeks. If there is no SPC endpoint assessment prior to 52 weeks, the subject will be considered not meeting the criteria.

The primary endpoint will also be analyzed for the subgroups defined by demographic characteristics, baseline comorbidities, rheumatoid arthritis, or surgical site. The treatment group comparisons after controlling each of these factors will be conducted by stratified analyses using the Mantel Haenszel method as sensitivity analyses

### 9.6.3 Key Secondary Endpoint

The key secondary efficacy endpoint will be the proportion of subjects who meet the following criteria for the CT radiographic fusion success at 52 weeks:

- Radiographic evidence of fusion by CT scan ( $\geq 50\%$  bone bridging across the joint space for the full complement of joints in the absence of secondary surgical or nonsurgical interventions intended to promote fusion)

Non-inferiority and superiority will be assessed in a similar manner to the primary efficacy endpoint, and each test will be conducted according to the fixed-sequence procedure described in Section 9.6.1.

### 9.6.4 Secondary Endpoint(s)

The following secondary efficacy endpoints will be assessed without multiplicity adjustments.

- Proportion of subjects achieving CT radiographic fusion success at 12 and 24 weeks (in the absence of secondary surgical or nonsurgical interventions intended to promote fusion)
- Change from baseline in pain on weight-bearing at fusion site at 12, 24, and 52 weeks ( $\geq 20$  mm reduction from baseline on 100 mm VAS)
- ABG harvest site pain at 2, 6, 12, 24 and 52 weeks ( $< 20$  mm on 100 mm VAS)
- Change from baseline in FAAM-ADL at 12, 24 and 52 weeks
- SPC at 12 and 24 weeks
- Change from baseline in Short Form-12 (SF-12) at 24 and 52 weeks

The difference of the proportions of subjects achieving CT radiographic fusion success between treatment groups will be estimated with the 2-sided 90% confidence interval at 12 and 24 weeks. Similarly, the difference of the proportions of subjects meeting all the criteria for SPC between treatment groups will also be estimated at 12 and 24 weeks.

The change from baseline in weight-bearing pain at fusion site at 12, 24 and 52 weeks will be analyzed by the repeated-measures ANCOVA. The proportion of subjects achieving  $\geq 20$  mm reduction from baseline in weight-bearing pain at fusion site will also be summarized by treatment group at each visit.

The change from baseline in FAAM-ADL at 12, 24 and 52 weeks will be analyzed by a repeated-measures analysis of covariance (ANCOVA) model that includes treatment, time, treatment-by-time interaction, baseline score, and other relevant factors or covariates on the observed data. In addition, the proportion of subjects achieving  $\geq 8$  points improvement from baseline in FAAM-ADL will be summarized by treatment group at each visit.

The ABG harvest site pain at 2, 6, 12, 24 and 52 weeks will be summarized for the ABG group. The proportion of subjects with < 20 mm in ABG harvest site pain will also be summarized at each visit.

The change from baseline in SF-12 scores at 24 and 52 weeks will be analyzed by the repeated measures ANCOVA.

## **9.7 Safety**

### **9.7.1 General Considerations**

Safety parameters will be evaluated for the safety analysis data set.

### **9.7.2 Adverse Events**

A treatment emergent adverse event (TEAE) will be an AE that occurs at the start of surgery and thereafter. An AE overview summary table will be prepared for the safety analysis set. It will display the number and percentage of subjects reporting an AE and the number of events reported for each treatment group. The following categories will be displayed:

- Unanticipated Adverse Device Effects
- SAEs
- Device related SAEs
- Procedure related SAEs
- Device related AEs
- Procedure related AEs
- Any TEAEs

Number and percentage of subjects reporting the following types of TEAEs will be summarized by MedDRA SOC (alphabetically) and PT (in decreasing frequency of occurrence):

- Unanticipated Adverse Device Effects
- SAEs
- Device related SAEs
- Procedure related SAEs
- Device related AEs
- Procedure related AEs
- Any TEAEs

### 9.7.3 Other Safety Variables

Descriptive statistics of subsidence, device migration, nonunion, osteolysis and/or heterotopic ossification in the area surrounding the implant site by radiographic assessment, clinical laboratory testing and antibody monitoring will be presented for the safety analysis set by treatment group.

Number and percentage of subjects reporting the following events will be summarized:

- Any secondary surgical interventions including revisions, removals, reoperations, or supplemental fixations
- Secondary surgical intervention related to the graft material including revisions, removals, reoperations, or supplemental fixations

### 9.8 Pharmacokinetic Assessment

The PK analysis will be performed by Department of Experimental Medicine, Ferring Pharmaceuticals A/S. The PK parameters will be calculated by non-compartmental analysis (NCA) using the software WinNonlin®Phoenix v. 6.4 (Pharsight Corporation, US). Plasma concentration values below LLOQ and missing values (e.g. no blood sample collected or no value obtained at analysis) will be excluded from the NCA and the number of observations adjusted accordingly. No formal analysis of “outliers” is planned.

PK parameters will be estimated based on measurements Pre procedure (baseline) to the last day of assessment Day 15 after fusion procedure. From the plasma concentration-time data of B2A, the following parameters will be estimated, if possible: AUC, AUCt, % AUC extrap, Cmax, Tmax, t1/2, lamda z, CL/F, Vz/F.

Actual sampling time points relative to dosing will be used for the NCA and on the individual plots of plasma concentration versus time. Values below LLOQ will be represented as LLOQ/2 in the plots.

PK parameters will be presented with number of measurements, number of missing data, mean, standard deviation, median, minimum, maximum, geometric mean, and coefficient of variation (CV [%]) on geometric mean (for AUC and Cmax). For tmax the geometric mean and the CV (%) will be omitted.

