For preparation of implant-ready AMPLEX by following the instructions in IFU, the lyophilized drug product (DP) is reconstituted in sterile water for injection (WFI). In-use stability of the reconstituted drug product has been demonstrated by measuring purity of the solution following reconstitution over a six (6) hour period. After reconstitution, a defined volume of B2A solution is withdrawn, added to the granules (BVF) and mixed according to the IFU. Implant-ready AMPLEX, with 0.225mg B2A/cm^3 granules should be used within four (4) hours of preparation.

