### **5.1.3 Investigational Device and Non-Investigational Material**

The aggregate volume of the investigational device (AMPLEX) or control material (ABG) utilized in index joints will be at the discretion of the surgeon, provided the joint space(s) can be adequately filled with graft material according to the following parameters:

- Single hindfoot joint fusion: up to 5 cm^3
- Double or triple hindfoot fusion: each individual joint up to 5 cm^3, but overall, not more than 10 cm^3 for the full complement of joints
- Ankle fusion: up to 10 cm^3

ABG will be obtained from a location other than the graft site, for example, the calcaneus, proximal tibia, distal tibia, or iliac crest using standard surgical procedure. The selection of the ABG harvest site will be at the discretion of the surgeon and based on medical judgment. The harvested bone will be cleaned of soft tissue and morselized. The volume of ABG harvested for treatment will be measured using a syringe and the amount implanted, including the treated joint(s) recorded.

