### 6.1.3 Day of Surgery

Once eligibility is confirmed the subject can be randomized, but the subject will not be notified of randomization result until after the surgery.

The following assessments/activities will be performed on the day of surgery:

- Verify subject meets eligibility criteria
- Record date and time of hospital admission
- Record medical history and comorbidities since screening
- Record vital signs
- Identify the arthrodesis site(s) / index joint(s)
- Collect urine sample for pregnancy test from female subjects of childbearing potential (within 24 hours prior to procedure)
- Record volume of blood loss and blood use during surgery
- Record the number and type of screws and screw systems used during surgery
- Record operation start and end time (incision to closure)
- Measure and record the volume of AMPLEX implanted per joint and identify the joint; and record the amount remaining after surgery. For ABG, record the volume harvested for treatment, implanted per joint, identify the joint, and record the amount remaining after surgery.
- Perform specific intraoperative data collection
- Record any protocol deviations
- Record all concomitant medications including (anesthesia) taken since the screening visit
- Record any AEs experienced from time of screening

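### PK Cmax and AUC are summarised without reference to B2A dose, although dose follows graft volume and the permitted ceilings differ two-fold

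*Protocol*

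**What the plan says.** The protocol fixes the peptide concentration but not the dose. Section 5.1.1 describes the prepared device "with 0.225mg B2A/cm 3 granules". Section 5.1.3 says that the volume of graft "utilized in index joints will be at the discretion of the surgeon", subject to ceilings:

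- "Single hindfoot joint fusion: up to 5 cm 3"
- where two or three hindfoot joints are fused, "each individual joint up to 5 cm 3 , but overall, not more than 10 cm 3 for the full complement of joints"
- for ankle fusion, 10 cm³.

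No minimum volume is given. Section 6.1.3 tells sites to "Measure and record the volume of AMPLEX implanted per joint and identify the joint".

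Section 7.4 sets the PK subset at up to about 30 AMPLEX subjects, with at least 20 evaluable. The only rule on its composition is that both sexes be represented. Samples are taken before the procedure and on Days 1, 2, 4, 7 and 15.

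Section 9.8 describes the analysis: "PK parameters will be presented with number of measurements, number of missing data, mean, standard deviation, median", followed by the minimum, maximum and geometric mean, and a CV on the geometric mean for AUC and Cmax. It also plans CL/F, Vz/F and individual concentration-time plots. Parameters are estimated only where the data allow, and values below the LLOQ are left out of the non-compartmental analysis. Dose normalisation and grouping by volume or procedure are not mentioned. SAP Section 2.2.5 places the PK analysis outside the SAP's scope, so the SAP adds nothing on this point.

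**The concern.** The PK part is descriptive, and its product is a small table of Cmax and AUC. In a fixed-dose study such a table describes one dose. Here each subject's dose is set by the size and number of joints filled, and nothing controls the mix of procedures in the subset.

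If plasma exposure rises with dose, three things follow:

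- The pooled mean and geometric mean move with the share of large grafts, which is a matter of recruitment, not of pharmacology.
- Both lie below the corresponding value at the largest permitted volume.
- The CV combines between-subject PK variability with the spread in dose.

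A reader could not separate these components from the planned output, and could not tell whether anyone near 10 cm³ was sampled. What is at stake is how far the PK results can be interpreted. No test or decision rule in the trial depends on them.

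**Working it through.** **Dose (documented inputs).** Dose D = 0.225 mg/cm³ × volume V.

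- Check against the plan's own figure: Section 5.1.1 says that one 2.8 mg vial suffices for both 5 cm³ granule vials. 0.225 × 10 = 2.25 mg, which is within 2.8 mg, so the figures agree.
- At the 5 cm³ ceiling, D = 0.225 × 5 = 1.125 mg. At the 10 cm³ ceiling, D = 2.25 mg. The ratio is 2.
- Below the ceilings the volumes are assumptions. For example, 2 cm³ gives 0.45 mg, and 2.25/0.45 = 5.

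**What CL/F and Vz/F adjust.** CL/F = D/AUC, where the protocol defines AUC as extrapolated to infinity, so it needs the terminal rate constant. Vz/F = (CL/F)/λz needs it too. Neither yields a dose-adjusted Cmax or AUCt. A subject without an estimable terminal phase has neither CL/F nor Vz/F.

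**Effect of pooling (assumed inputs).** The documents give no volume distribution and no expected CV, so both are assumed. Let exposure be proportional to D, and let log dose be independent of log dose-normalised exposure. Then:

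- pooled mean ÷ mean at 10 cm³ = E[V]/10
- pooled geometric CV = √(exp(ln(1 + CV²) + Var(ln V)) − 1), where CV is the dose-normalised CV.

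Var(ln V) for each assumed distribution:

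- Half at 5 and half at 10 cm³: (ln 2 / 2)² = 0.120.
- Uniform on (a, b): the mean of ln V is [v(ln v − 1)] and the mean of (ln V)² is [v((ln v)² − 2 ln v + 2)], each taken from a to b and divided by b − a. For 4–10 cm³: 3.7284 − 1.9134² = 0.067. For 2–10 cm³: 3.0974 − 1.7049² = 0.191.

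Worked example, half at 5 and half at 10 cm³, CV 30%: ln(1.09) = 0.086; 0.086 + 0.120 = 0.206; √(exp(0.206) − 1) = 0.48. The mean ratio is 7.5/10 = 0.75.

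| Assumed volumes | Mean vs 10 cm³ | Geometric mean vs 10 cm³ | CV 30% becomes | CV 50% becomes | CV 80% becomes |
|---|---|---|---|---|---|
| Uniform 4–10 cm³ | 0.70 | 0.68 | 41% | 58% | 87% |
| Half 5, half 10 cm³ | 0.75 | 0.71 | 48% | 64% | 92% |
| Uniform 2–10 cm³ | 0.60 | 0.55 | 56% | 72% | 99% |

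If all volumes were equal, Var(ln V) would be 0 and the CV would be unchanged.

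**Case mix alone.** With volumes only at 5 or 10 cm³ and a share p at 10 cm³, the mean ratio is p + (1 − p)/2. This is 0.60, 0.75 and 0.90 for p = 20%, 50% and 80%.

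**Departure from proportionality.** Let exposure vary as D^b, with volumes uniform on 2–10 cm³ and a CV of 50%. Var(ln V) is multiplied by b², and the mean ratio becomes E[V^b]/10^b.

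| b | Mean vs 10 cm³ | CV 50% becomes |
|---|---|---|
| 1 | 0.60 | 72% |
| 0.5 | 0.76 | 56% |
| 0 | 1.00 | 50% |

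With b = 0 there is no distortion.

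**The case against.** Several parts of the case against this point stand.

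- **Size of the dose range.** A reader might infer that doses will vary several-fold. The documents show only a two-fold difference in ceilings. A wider spread is permitted, because there is no minimum, but it is an assumption.
- **Direction of the effect.** A reader might conclude that the CV is inflated and that exposure at 10 cm³ is understated. Both need exposure to rise with dose. The documents do not say that it does, and they describe the peptide as bound to the granules without saying how release scales with volume.
- **Make-up of the subset.** Nothing shows that small single-joint grafts will dominate it. The documents give no procedure mix.
- **Link to the safety narrative.** Table 1 of the protocol attributes its statement about low circulating B2A to preclinical testing. It does not present the PK subset as support for that statement.
- **Planned outputs.** The maximum and the individual plots will show high exposures, and CL/F and Vz/F contain dose. Any understatement would concern the mean and geometric mean only.
- **Silence and timing.** Section 9.8 does not say how subjects are grouped, and dose-normalised rows could be added at reporting because nothing confirmatory depends on them.

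These arguments narrow the point but do not remove it. The maximum and the plots are not tied to dose, Cmax and AUCt are not adjusted by any planned parameter, and CL/F and Vz/F may be missing for some subjects. If exposure turned out not to depend on dose, the listed summaries would not show that either.

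**Conclusion.** The point holds as a cheap improvement. It is documented that B2A dose follows implanted volume, that the ceilings differ two-fold, and that Section 9.8 specifies neither dose normalisation nor a display by volume.

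The consequence is conditional on exposure rising with dose. Under proportionality and the assumed volume distributions, a dose-normalised CV of 30% would be reported as about 41%, 48% or 56%, with the pooled mean at 70%, 75% or 60% of the 10 cm³ mean respectively. A larger underlying CV makes the relative inflation smaller. With an exposure-dose exponent of 0.5, uniform 2–10 cm³ volumes and a CV of 50%, the figures are 56% and 76%. With an exponent of 0 there is no effect. The documents do not settle which case applies.

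No efficacy conclusion, type I error or power figure is affected. The point implies no view on which graft volume is appropriate.

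**What to change.** In Protocol Section 9.8, or in the PK analysis plan if one exists:

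- Add dose-normalised Cmax/D, AUCt/D and AUC/D, with D equal to each subject's recorded implanted volume times 0.225 mg/cm³.
- Add either a plot of exposure against implanted dose, or raw Cmax and AUC by the volume categories already used in SAP Section 8.1.1 (up to 5 cm³; above 5 to 10 cm³).

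No new data are needed: Section 6.1.3 already has the volume recorded per joint, and CL/F already requires each subject's dose. The cost is a few table rows and perhaps one figure. With 20 to 30 subjects the volume subgroups will be imprecise, so they should be presented as descriptive only. The plot avoids splitting the subset.
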